1. BACKGROUND AND SCIENTIFIC RATIONALE

Molar–Incisor Hypomineralization (MIH) is a qualitative enamel defect affecting 10–20% of European children. MIH molars show porosity, post-eruptive breakdown, and hypersensitivity, reducing the predictability of conventional restorative treatments. Current therapy options—composites, resin-modified glass ionomers, stainless-steel crowns—face limitations such as polymerization shrinkage, marginal degradation, and short service life.

Advances in nanotechnology have introduced graphene-based biomaterials featuring high flexural strength (>180 MPa), biocompatibility, and favorable esthetics. Graphene-reinforced CAD/CAM polymers (e.g., G-CAM®) permit minimally invasive adhesive restorations that may improve outcomes in MIH-affected posterior teeth.

This study prospectively evaluates the 12-month clinical performance of graphene-reinforced CAD/CAM indirect restorations in adolescent MIH patients.

2. STUDY OBJECTIVES AND HYPOTHESIS

Primary Hypothesis

Graphene-reinforced CAD/CAM indirect restorations provide high clinical acceptability at 12 months, according to predefined FDI criteria, while reducing postoperative hypersensitivity relative to baseline and preserving structural tooth integrity.

Primary Objective

Evaluate the overall clinical performance of graphene-reinforced CAD/CAM inlays/onlays/overlays in MIH-affected molars at 12 months.

Secondary Objectives

- Assess FDI domain scores: marginal integrity, surface roughness, color stability, fractures, proximal contacts, occlusion/function, and soft-tissue response.
- Measure postoperative sensitivity using VAS.
- Assess patient-reported satisfaction.
- Evaluate structural preservation via pre/post 3D scans.
- Measure restoration survival (Kaplan–Meier).
- Assess workflow efficiency (chair time, need for adjustments).

3. STUDY DESIGN

A prospective, single-arm, monocentric, interventional clinical study with 12-month follow-up.

Number of participants: 30 adolescents (10–16 years old).

Study duration: 18 months.

Follow-up: Baseline, 48 h, 1 m, 3 m, 6 m, 12 m.

4. STUDY POPULATION

Inclusion Criteria

- Adolescents aged 10–16.
- Permanent molars with moderate/severe MIH (EAPD).
- Vital, restorable teeth.
- Ability to attend follow-ups. • Informed consent + minor assent.

Exclusion Criteria

- Fluorosis, amelogenesis imperfecta, other enamel anomalies.
- Severe bruxism.
- Extensive active caries or irreversible pulpitis.
- Systemic diseases affecting enamel/healing.
- Allergy to dental materials.
- Analgesics/AINE <24 h before baseline sensitivity assessment.

5. STUDY INTERVENTION

All participants undergo:

1. Baseline diagnostics and imaging
2. Minimally invasive cavity preparation
3. Composite base build-up if required
4. CAD/CAM fabrication of graphene-reinforced polymer inlay/onlay/overlay
5. Adhesive cementation under rubber dam
6. Finishing and occlusal evaluation

Material used: **Graphene-reinforced CAD/CAM polymer block (G-CAM®)**

6. OUTCOME MEASURES

Primary Outcomes

1. **FDI Global Acceptability (Success = all domains ≤ 3)** at 12 months
2. **Postoperative sensitivity (VAS 0–10)** at baseline, 48 h, 1, 3, 6, 12 months

Secondary Outcomes

- Patient satisfaction (Likert 1–5)
- Structural preservation (volumetric analysis of 3D scans)
- Vitality retention

- Restoration survival (Kaplan–Meier)
- Workflow efficiency (chair time, adjustments)

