9. STATISTICAL ANALYSIS PLAN (SAP)

Sample Size

30 participants (27 required for detecting a ≥ 2 -point VAS reduction; $\beta=0.80$, $\alpha=0.05$).

Analysis Methods

Descriptive Statistics

Mean \pm SD, median [IQR], and proportions.

Primary Analyses

- **FDI scores (ordinal):**

Friedman repeated-measures test + Holm correction

or ordinal mixed-effects model (time = fixed, participant = random)

- **VAS sensitivity (continuous):**

Linear mixed-effects model

or repeated-measures ANOVA (Greenhouse-Geisser correction)

Survival Analysis

- Kaplan–Meier survival curve
- Failure = debonding or fracture requiring replacement

Performance Threshold Tests

- FDI success proportion at 12 months with 95% CI
- One-sample binomial test vs threshold $\geq 80\%$
- Mean VAS reduction ≥ 2 points with CI >0

Missing Data

- Missing-at-random assumption
- Mixed models inherently robust; no imputation planned

Interim Analysis

None planned.

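### The FDI methods listed as primary need repeated scores, but the only FDI time stated is 12 months, and the analysis that fits that endpoint is listed elsewhere

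*Protocol*

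**What the plan says.** - **Outcome (Section 6, Primary Outcomes).** The first primary outcome is "FDI Global Acceptability (Success = all domains ≤ 3", with 12 months as its time. It is a binary result. The next line gives the VAS sensitivity outcome a full list of times: "at baseline, 48 h, 1, 3, 6, 12 months". The secondary outcomes contain no FDI entry.
- **Objective (Section 2, Secondary Objectives).** "Assess FDI domain scores: marginal integrity, surface roughness, color stability" and further domains are listed, without times.
- **Visits (Section 3).** "Follow-up: Baseline, 48 h, 1 m, 3 m, 6 m, 12 m". The section does not say what is measured at each visit.
- **Primary methods (Section 9, Primary Analyses).** For FDI scores, treated as ordinal, the choice is "Friedman repeated-measures test + Holm correction" "or ordinal mixed-effects model (time = fixed, participant = random").
- **Threshold tests (Section 9, Performance Threshold Tests).** Here stands "FDI success proportion at 12 months with 95% CI", followed by a one-sample binomial test against 80%.

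**The concern.** The outcome section and the primary-analysis section describe two different quantities. Section 6 describes a binary success at one time. The methods called primary in Section 9 describe ordinal scores followed over time.

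Two things follow. A site that takes Section 6 as its guide may collect one FDI assessment, and then neither of the named primary methods can be run. And even if FDI is scored at every visit, a test of change over time does not answer whether a high proportion of restorations is acceptable at 12 months, which is what the primary hypothesis in Section 2 asks. At stake is whether the analysis labelled primary estimates the primary endpoint, and whether the data for the time analysis will exist. FDI scores not taken chairside at an early visit cannot be fully recovered later.

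**Working it through.** The protocol gives no figure for FDI to reproduce. Its sample size (27 required, 30 enrolled) is set for the VAS reduction and does not enter here.

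**Inputs**
- FDI times stated: 1 (12 months; Section 6).
- VAS times stated: 6 (Section 6).
- Visits: 6 (Section 3). One is baseline. Section 5 puts baseline diagnostics before preparation and cementation, so 5 visits are post-cementation, taking the 48 h visit as counted from cementation.
- Participants: 30 (Section 3).

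**Friedman test with k time points.** Degrees of freedom are k − 1, and the number of pairwise contrasts for Holm is k(k − 1)/2.

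| FDI times scored | k | df | Pairwise contrasts |
|---|---|---|---|
| 12 months only (as stated) | 1 | 0 | 0 |
| All 5 post-cementation visits | 5 | 4 | 10 |
| All 6 visits, with baseline | 6 | 5 | 15 |

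The statistic itself shows the first row. It is 12/(nk(k + 1)) × ΣR² − 3n(k + 1), where R is the rank sum at each time. With k = 1 every participant has rank 1, so R = n = 30, and the value is 12/(30 × 1 × 2) × 900 − 3 × 30 × 2 = 180 − 180 = 0, whatever the scores are.

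**Ordinal mixed model.** With one time, the time term is constant and cannot be told apart from the thresholds of the ordinal model. No time effect can be estimated.

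**Baseline as a second time.** In the last row, 15 − 10 = 5 contrasts involve baseline. No restoration exists then, so its margins, fractures or contacts cannot be scored. Adding baseline does not rescue the time analysis. The protocol does not say that the FDI time factor starts after cementation.

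**The analysis that does fit.** The binomial test needs one result per participant. Assume n = 30, all evaluated, one restoration each, and a one-sided 0.05 level (the protocol does not state sidedness). Tested against 80%, the rule is success at 28 or more of 30, with an exact type I error of 0.044. Power is 0.41 if the true success rate is 0.90 and 0.81 if it is 0.95. So the test can be run on a single 12-month score and matches the Section 6 outcome.

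**The case against.** The strongest reply is that Section 6 fixes the time of an endpoint and is not an assessment schedule. Section 2 has FDI domain scores as a separate objective without a time limit, Section 3 provides six visits, and the choice of repeated-measures methods suggests that repeated scoring was intended. Section 9 also holds an analysis that fits the binary endpoint. Much of this stands, and it limits what can be said:

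- A reader might infer that FDI is scheduled at 12 months only. The document does not say so. It states no other time, which is less.
- A reader might infer that the primary FDI endpoint cannot be analysed. It can, by the proportion and binomial test.
- A reader might infer that color stability cannot be assessed without an early FDI score. It is listed as one domain to be scored, and Section 8 plans standardized photos at follow-up, which may serve as a reference.
- A reader might object that a poor 12-month score cannot be traced to wear rather than placement. Neither the primary hypothesis nor the primary objective asks for that.
- A reader might count lost assessments as 4 visits × 30 participants = 120. That takes one restoration per participant, which is not stated, and assumes that the other visits go unscored.
- A reader might add that participants lost before month 12 give no FDI information. That holds only if FDI is scored once, and scoring at earlier visits would still not supply their 12-month result.

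What the reply does not remove is the conflict on the page. If repeated scoring was intended, its visits are not written down. On either reading, the methods under *Primary Analyses* do not analyse the binary 12-month outcome. Nor is this a detail left for a separate analysis plan: assessment times belong in the protocol, and Section 9 itself fixes the methods.

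**Conclusion.** The point holds in this form: the protocol states one FDI time, its primary FDI methods need several, and those methods do not address the binary endpoint. On the stated time alone, Friedman has 0 degrees of freedom and 0 contrasts, and the mixed model has no time effect to estimate. The analysis that suits the endpoint is present but not labelled as primary.

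This is an inconsistency that should be corrected. It is not a flaw that leaves the trial without a usable FDI result. The conclusion rests on reading Section 6 as the only statement of FDI times, which a check of Sections 2, 3, 8 and 9 supports, and on baseline being pre-operative, as Section 5 indicates. It does not depend on the number of restorations per participant. The power figures for the binomial test do, and they also depend on the assumed one-sided level.

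**What to change.** **Section 6.** State the existing post-cementation visits at which the FDI domains are scored. Include an early post-cementation reference (48 h or 1 month, for example) and 12 months. Keep 12-month success as the endpoint.

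**Section 9.**
- Move the 12-month success proportion with its 95% CI and the binomial test against 80% to *Primary Analyses*, as the primary FDI analysis.
- Make the repeated-measures analysis of the ordinal domain scores secondary.
- State that its time factor starts at the early post-cementation reference and leaves out the pre-operative baseline.

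**Cost.** A few minutes of scoring at visits already planned, and a change of protocol wording. No visits are added. The change to Section 6 is fully effective only if made before the early visits have passed. The change to Section 9 needs no new data, but should be made before results are seen.

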7. SAFETY AND ADVERSE EVENTS

Adverse events include:

- Persistent pain >72 h
- Severe hypersensitivity (VAS ≥ 7)
- Soft-tissue inflammation
- Partial or total restoration failure
- Complications requiring reintervention

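### FDI success is judged on the month-12 score alone, so a restoration repaired in place after a fracture or partial failure can count as a primary success and not as a survival failure; for debonding the survival rule has two readings

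*Protocol*

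**What the plan says.** - **Primary outcome (Protocol Section 6).** Success on the FDI criteria is "Success = all domains ≤ 3", judged at 12 months. Nothing is said about a restoration that was treated again before that visit.
- **Analysis of that outcome (Section 9, Performance Threshold Tests).** The plan reports "FDI success proportion at 12 months with 95% CI" and applies a "One-sample binomial test vs threshold" of 80%. The sidedness of the test is not stated.
- **Survival rule (Section 9, Survival Analysis).** "Failure = debonding or fracture requiring replacement".
- **Adverse events (Section 7).** The list includes "Partial or total restoration failure" and "Complications requiring reintervention". Neither is linked to FDI success or to survival.
- **Visits (Section 3).** There are visits at 48 hours and at 1, 3 and 6 months, so a failure can be found and corrected before the month-12 score is taken.

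**The concern.** The study is meant to show how this material performs clinically over its 12-month follow-up. A score taken after a repair reflects the repair as well as the restoration. Under the stated definition, a restoration that failed in part and was put right cannot be told apart, in the main proportion, from one that never needed attention.

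The effect has one direction. Treating such restorations as unsuccessful can lower the success count but never raise it. The study has a single arm and a fixed threshold of 80%, so no comparator receives the same leniency. What is at stake is whether the claim of exceeding 80% refers to the restoration as placed or to the restoration plus any rescue.

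This is not a missing-data problem. A restoration repaired in place has an observed month-12 score, so the missing-at-random statement in Section 9 does not touch it.

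**Working it through.** **Step 1. Apply the stated rules to each course of events.** In each row, assume that the original piece is still in place and that all month-12 domains are 3 or lower.

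| Event before month 12 | Section 7 | FDI success (Sections 6 and 9) | Survival rule (Section 9) |
|---|---|---|---|
| Fracture or partial failure, repaired in place | adverse event | success | no failure, as nothing was replaced |
| Debonding, recemented; replacement qualifier read as covering debonding | adverse event | success | no failure |
| Debonding, recemented; qualifier read as covering fracture only | adverse event | success | failure |

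The first row follows from the text without any choice of reading. The second and third rows describe the same event under the two readings of the survival rule. Under one it escapes both endpoints. Under the other it is a survival failure and an FDI success at once.

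**Step 2. The plan's own figure.** Section 9 gives "30 participants (27 required for detecting a" VAS fall of two points or more, with α = 0.05 and 0.80 printed as β, read here as power. The SD of the change is not given, so 27 cannot be reproduced. Solved backwards with a two-sided normal approximation, n = (SD × (1.960 + 0.842) / 2)², which gives SD = 2 × √27 / 2.802 ≈ 3.71. The figure concerns the VAS only. No sample size is stated for the FDI test, so its pass mark has to be derived.

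**Step 3. Pass mark of the test against 80%.** Assumptions: one restoration per participant, all 30 evaluable, exact one-sided test. The p-value for r successes is the sum over k = r to 30 of C(30,k) × 0.8^k × 0.2^(30−k).

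- k = 30: 0.8^30 = 0.0012
- k = 29: 30 × 0.2 × 0.8^29 = 0.0093, so P(X ≥ 29) = 0.0105
- k = 28: 435 × 0.04 × 0.8^28 = 0.0337, so P(X ≥ 28) = 0.0442
- k = 27: 4060 × 0.008 × 0.8^27 = 0.0785, so P(X ≥ 27) = 0.1227

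The pass mark is 28/30 at one-sided 5% and 29/30 at one-sided 2.5%. With 27 evaluable it is 26/27 at either level (p=0.0187; 25/27 gives 0.0718).

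**Step 4. Effect of reclassification.** Each restoration moves the proportion by 1/30 = 3.3 percentage points. At one-sided 5%, reclassifying one of 28 successes (28 to 27) or two of 29 (29 to 27) loses the result. At one-sided 2.5% the same holds for one of 29 (29 to 28) or two of 30 (30 to 28).

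**Step 5. A range away from the cut-off.** The documents give no repair rate, so the shares here are assumed. Let the true proportion that succeeds without reintervention be exactly 80%, and let a further share q be repaired or recemented and then score 3 or lower throughout. The chance of passing is P(X ≥ pass mark) with n = 30 and success probability 0.80 + q.

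| q | 28/30 rule | 29/30 rule |
|---|---|---|
| 0 | 4.4% | 1.1% |
| 3% | 9.5% | 2.7% |
| 5% | 15.1% | 4.8% |
| 10% | 41.1% | 18.4% |

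**The case against.** **The hypothesis in Section 2 speaks of acceptability at 12 months.** A month-12 status endpoint fits that wording, and success free of reintervention is a stricter, different endpoint. This has force: the present definition is coherent as a measure of status. It does not remove the one-directional effect when the proportion is used to judge the material against 80%.

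**Section 7 is a safety list, not an efficacy classification.** This is correct. A reader might infer that the protocol contradicts itself by calling the same event a failure and a success. The text does not go that far: a restoration can have an adverse event and still be acceptable later. What is missing is a stated link between the sections.

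**The events are captured elsewhere.** Reinterventions appear as adverse events. FDI scores are also analysed over time by a Friedman test or an ordinal mixed model, so a defect scored at an interim visit can enter there. This limits the harm but leaves the tested proportion unchanged.

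**A recemented restoration may not escape the survival rule.** A reader might infer that it certainly does. The documents do not support that, because the wording can equally be read as counting every debonding as a failure.

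**The 28/30 example sits on the cut-off and assumes a sidedness.** Both points are true, which is why the other pass marks and the assumed range are shown.

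**A separate SAP may settle this.** It may add detail, but the success definition and the survival rule are fixed in this protocol, and the point concerns what they state.

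**Conclusion.** The point holds for fracture and partial failure repaired in place: as written, such a restoration is a primary success if its month-12 scores allow, and it is not a survival failure. For debonding the finding is an ambiguity with an unsatisfactory result on either reading.

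A reader might infer that every rescued restoration becomes a success, or that the protocol expressly says so. Neither is supported. Success still depends on every month-12 domain being 3 or lower, and the protocol is silent on reintervention.

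The size depends on how often repairs occur, which the documents do not give. The test tolerates only two unsuccessful restorations in 30 at one-sided 5%, or one at one-sided 2.5%, so one or two reclassifications can decide it. This assumes one restoration per participant, 30 evaluable and an exact one-sided test. The change should be made, but the issue does not invalidate the design.

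**What to change.** - **Section 6.** Count as an FDI success only a restoration with all domains at 3 or lower at 12 months and no earlier recementation, repair or replacement for failure. Report the month-12 score regardless of reintervention as a secondary figure, so that the status measure is kept.
- **Section 9, Survival Analysis.** State whether the replacement condition applies to debonding as well as to fracture. Preferably count the first debonding as a survival event even if the piece is recemented.
- **Consistency.** Link the failure and reintervention entries in Section 7 to these two definitions, so that Sections 6, 7 and 9 classify the same event in a stated way.

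These changes concern how outcomes are classified, not how patients are treated. No new data item should be needed, since failures and reinterventions are already recorded as adverse events. The cost is a protocol amendment (Section 10 records ethics approval of version 3.0), and the success and survival proportions may come out slightly lower.

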7. SAFETY AND ADVERSE EVENTS

Adverse events include:

- Persistent pain >72 h
- Severe hypersensitivity (VAS ≥ 7)
- Soft-tissue inflammation
- Partial or total restoration failure
- Complications requiring reintervention

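### The VAS ≥ 7 adverse-event criterion takes no account of the child's baseline score, so pre-existing sensitivity can be counted as harm

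*Protocol*

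**What the plan says.** Section 7 of the protocol gives a list that opens with "Adverse events include" and has five items. One is "Severe hypersensitivity (VAS ≥ 7"). It carries no baseline reference, no requirement that the sensitivity be new or worse, and no time window. Another item is "Persistent pain >72 h", which names neither a VAS level nor a baseline.

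Four other places bear on how that criterion works:

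- Section 1 describes the condition: "MIH molars show porosity, post-eruptive breakdown, and hypersensitivity".
- Section 4 sets neither a minimum nor a maximum baseline VAS. Its only criterion about the sensitivity measurement is the exclusion "Analgesics/AINE <24 h before baseline sensitivity assessment".
- Section 6 makes the 0–10 VAS a primary outcome, measured "at baseline, 48 h, 1, 3, 6, 12 months".
- Sections 2 and 9 judge that outcome as a change. The hypothesis speaks of "reducing postoperative hypersensitivity relative to baseline", and the performance threshold is "Mean VAS reduction ≥ 2 points with CI >0".

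Section 3 describes a single-arm study of 30 adolescents.

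**The concern.** One scale is read in two ways: relative to the child's own baseline for benefit, and as an absolute level for harm. With no control arm, the child's baseline is the only reference that can separate sensitivity present before the restoration from sensitivity that arose after it. An absolute cut-off discards that reference.

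Two kinds of misclassification follow. A child who enters at 7 or more and does not change, or improves but stays at 7 or more, is logged under the safety heading. A child whose sensitivity rises after preparation or cementation but stays below 7 does not meet the criterion. The count for this item then mixes the baseline severity of those enrolled with the effect of the procedure. With only 30 children, a few such cases visibly change the reported figure.

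**Working it through.** **No plan figure to reproduce.** The protocol states no expected adverse-event frequency and no VAS mean or SD. The check has two parts: what the rule does to each possible pair of scores, and how often that might happen under stated assumptions.

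**Part 1: the rule applied to every pair.** Inputs are the 0–10 scale (Section 6) and the rule that a follow-up score of 7 or more is an event (Section 7). Whole-number scores are assumed, giving 11 × 11 = 121 pairs (baseline → follow-up).

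- Flagged pairs: 4 follow-up values × 11 baselines = 44.
- Flagged and no worse than baseline: follow-up 7 with baseline 7–10 (4 pairs), 8 with 8–10 (3), 9 with 9–10 (2) and 10 with 10 (1), so 4 + 3 + 2 + 1 = 10. Four are unchanged (7→7, 8→8, 9→9, 10→10) and six are improved.
- Flagged and improved by 2 or more: 9→7, 10→7 and 10→8. These need a baseline of 9 or 10.
- Worsened by 2 or more: 45 pairs, of which 15 end below 7 and are not flagged. Examples are 0→6, 1→6, 2→6 and 0→5.

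These counts show which cases the rule sorts wrongly. They are not probabilities.

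**Part 2: illustrative frequency.** All inputs here are assumptions: baseline normal with SD 2, change with mean −2 and drawn independently of baseline, scores rounded and clipped to 0–10.

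The share at 7 or more before treatment is P(baseline ≥ 6.5 before rounding) = 1 − Φ((6.5 − mean)/2). For means 4, 5, 6 and 7 this is 1 − Φ(1.25), 1 − Φ(0.75), 1 − Φ(0.25) and 1 − Φ(−0.25), or about 11%, 23%, 40% and 60%. The other rows come from simulating 2,000,000 children per scenario with an SD of change of 2.5.

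| Baseline mean | 4 | 5 | 6 | 7 |
|---|---|---|---|---|
| Already ≥ 7 before treatment | 11% | 23% | 40% | 60% |
| Of those flagged at a visit, no worse than baseline | 26% | 38% | 50% | 62% |
| Of all children, improved by ≥ 2 and flagged | 0.2% | 0.8% | 2.2% | 4.9% |
| Of those worse by ≥ 2, not flagged | 48% | 31% | 18% | 9% |
| Of all children, worse by ≥ 2 and not flagged | 3.9% | 2.5% | 1.4% | 0.6% |

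**Sensitivity to the SD of change.** Section 9 gives 27 children for a 2-point reduction at α = 0.05. It labels 0.80 as β, read here as power. A two-sided normal calculation implies SD = 2 × √27 / (1.960 + 0.842) ≈ 3.7, and the t version gives about 3.6. With 3.6, the second row falls to a range of 12% to 46%.

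**Sensitivity to the baseline.** Over baseline means of 4–8 and SDs of 1.5–2.5, the share already at 7 or more runs from about 5% to 84%. The share at 9 or more, who would still be flagged after an exact 2-point improvement, runs from about 0.1% to 42%.

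**The case against.** A fixed severity cut-off is a usable safety trigger, because it picks up every child with a high score whatever the cause. Restricting reports to sensitivity that emerged after treatment is a convention that a statistical analysis plan or safety manual could supply. Section 9 plans no test, rate comparison or stopping rule on adverse events. Change in VAS is itself a primary outcome analysed over time, so worsening enters the data whether or not it is called an adverse event. All of this stands, and it limits how much rests on the criterion. It does not remove the point: Section 7 itself fixes the definition, and that definition decides what is recorded during the trial.

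Four stronger readings are tempting, and the protocol does not support them.

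- **That a child made worse goes unreported.** The list is introduced as open. A child going from 0 to 6 could be logged under persistent pain, under reintervention, or as an unlisted event. Only the VAS criterion misses the case.
- **That a child improving from 9 to 7 meets the trial's definition of benefit and of harm at once.** The 2-point target is a group mean, and no individual response is defined. The case also needs a baseline of 9 or 10 and is uncommon in the main illustration: 4.9% × 30 ≈ 1.5 children at most per visit.
- **That the adverse-event rate as a whole describes who was enrolled.** The other four listed items do not depend on a VAS cut-off.
- **That the simulated shares estimate what will happen.** Every input is assumed. If children with high baselines improve more than others, the share flagged while no worse would be lower than shown.

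**Conclusion.** The point holds in a limited form. As written, the VAS criterion logs an adverse event for any child at 7 or more before treatment who is unchanged, or improved but still at 7 or more. It does not capture worsening that ends below 7. That follows from the text alone, and the unchanged child (8→8) shows it without relying on the 2-point target.

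The size cannot be determined from the protocol. The illustrative figures show only that the problem need not be negligible: a substantial minority, or even a majority, of flagged children could be no worse than at baseline, depending on the assumed baseline mean and SD of change. This is an inexpensive improvement to one safety item. It does not affect the validity of the primary analyses.

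**What to change.** In Section 7, relate the VAS criterion to the baseline score:

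1. Count a VAS of 7 or more as an adverse event only when it exceeds the child's own baseline.
2. List scores of 7 or more that are unchanged or improved from baseline separately.
3. Report increases from baseline that stay below 7 alongside, as a description, without setting a new clinical cut-off.

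The change concerns classification and reporting only. Clinical attention to any child with a high score stays as it is.

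The cost is a short addition to Section 7 and slightly more tabulation, using scores already scheduled at all six time points. The adverse-event count may change as a result. The rule should be settled before follow-up scores are classified.
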